1. OBJECTIVES

The objectives of our study are the following:

General:

- Determine the effectiveness of a protocolized treatment of specific physiotherapy for patients undergoing femoroacetabular syndrome by means of arthroscopy in pain, range of mobility and functionality.

Specific:

- Check how the age, level of physical activity prior to the study, sex, level of adherence to the program or body mass index of the subject influences the effectiveness of protocolized treatment of physiotherapy in patients surgically operated on femoroacetabular syndrome by arthroscopy.

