5.2. Dependent variables

The dependent variables of the study are the following:

Range of Mobility (ROM).

In the present study measurements will be made by goniometry of hip joint movement ranges. The goniometry is a technique of measurement of the angles created by the intersection of the longitudinal axes of the bones at the level of the joints.

These are continuous quantitative variables, measured in degrees with a range between 0° and 180°.

- a. ROM in hip flexion.
- b. ROM in hip extension.
- c. ROM in hip abduction.
- d. ROM in hip adduction.
- e. ROM in internal hip rotation.
- f. ROM in external rotation of the hip.

Orthopedic tests

The FAI will be checked through the performance of the Fabere, Fadir and Ober functional tests described below.

- a. **FABERE TEST:** The patient's hip is flexed, abducted and externally rotated by placing the external malleolus on the knee of the contralateral leg. The pelvis is

- stabilized and an overpressure is applied to the inside of the knee. It is positive if the pain in the buttock or groin is reproduced. Test with inter-evaluator reliability in Kappa values (95% CI) of 0.60.
- b. FADDIR TEST: Flexion, adduction and internal rotation test. The supine patient, the evaluator patiently brings the patient's hip up to 100° flexion and adduction while applying internal rotation. It is positive if pain in the groin is reproduced. Test with inter-evaluator reliability in Kappa values of 0.48.
 - c. OBER TEST: Patient in lateral decubitus position. The evaluator flexes the knee that is evaluated at 90° and abducts and extends the hip until it is level with the trunk. The evaluator lets the gravity bring the hip on adduction as possible. Test with inter-evaluator reliability of 0.90.

Variable intensity of pain

The Visual Analogue Scale (VAS) will be used. It is a continuous quantitative variable with a range between 0 and 10.

Evaluation functionality.

The modified Harris Scale will be used to the patient to evaluate the functionality of the hip and its interference in the activities of daily life. The patient will be evaluated with this scale prior to the surgical intervention and 14 weeks after the surgery.

6. STUDY GROUPS.

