The sample will be divided into 2 groups: Intervention Group and Control Group. The postoperative physiotherapeutic treatment protocol described will be applied to the intervention group. The non-intervention group will receive the nonspecific protocol of postoperative treatment for hip rehabilitation described by Gocen et al.

7. EVALUATION.

The evaluator is the person who will perform the pre and postsurgical measurements. He will be trained in the use of the goniometer and in the performance of orthopedic tests as well as in the material to be used. It will be located in the "Evaluation Room", with the material and conditions necessary to carry out the measurements. It will register and store the data for its later evaluation and statistical analysis.

The evaluator will be blinded with respect to the subject's belonging to the intervention or control group.

Data will be recorded at three times: before surgery, after 4 weeks and after 14 weeks of surgery. Immediate postoperative measurements will not be made, given that the clinical picture and tissue injury of the intervention could cause inaccurate results because a period of post-surgical wound stabilization has not elapsed.

These tests and measurements of variables will provide us with the degree of hip readjustment and its functionality, since they respond to the affected musculoskeletal structures both prior to the arthroscopy intervention due to the pathophysiology of the FAI, and after it for the wounds and surgical scars that are generated.

8. STUDY SEQUENCE.

A. Recruitment: it takes place before the surgery in the Traumatology clinic of Alicante Clinic (we attach authorization of the center to carry out the study) Two facultative specialists in orthopedic surgery and traumatology, transfer the information to the patient in written support about the characteristics of the study , purpose and form of follow-up, at the same time that they verify the eligibility of the subject according to the criteria of the study. Another member of the research team will independently check the eligibility of the subject in an evaluation session and will be responsible for performing the evaluations of the study variables before surgery, at 4 and 14 weeks after surgery. The evaluator will be present to resolve and clarify any doubts in this regard. After this, and with the acceptance of the patient to be part of the study, the informed consent will be signed.

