The statistical program that we will use will be SPSS v.20. To determine the sample size, a pilot study will be conducted with the same methodology as the original study to a group of 10 subjects. These subjects will be assigned to the same group. This pilot study will provide us with the estimates of the mean and variance of the response variable, thus being able to calculate the appropriate sample size by determining a minimum power value of 80% ($W > 80\%$) and a confidence level of 95% ($p < 0.05$).

The pilot sample will be part of the final sample to be studied if there are no changes in the protocol or in the variables to be measured.

The FAI is an important cause of coxarthrosis. Hip osteoarthritis is a pathology of high prevalence, with important socioeconomic repercussions. In Spain, 16% of the population over 20 years of age suffers, with a clear prevalence in women.

In a retrospective radiological study, Marín et al found around 70% the presence, on radiographs performed years before the intervention, of femoral and acetabular signs suggestive of femoroacetabular shock in children under 55 years who underwent total arthroplasty of hip. Other authors have reported values around 45% in patients pending intervention of hip prostheses with an age range between 30 and 82 years.

We consider it feasible to obtain a sample necessary for the present study (around 30 subjects per group) in view of the sample size of published articles on the effectiveness of conservative or postoperative treatment protocols for hip disorders and FAI and the high prevalence of FAI. The estimated time of obtaining the necessary sample will be around 6 months.

Descriptive analysis: A descriptive statistical analysis of all the variables will be carried out using frequency tables for the qualitative variables, and the minimum, maximum, average and standard deviation for the quantitative variables.

Inferential analysis: In relation to the inferential analysis, the statistical tests described below will be performed.

- a. Normal distribution test of Kolmogorov-Smirnov to identify the distribution of the samples.
- b. Levene test to check if the variances are homogeneous.

- c. ANOVA test (when the sample were are normal) or Kruskal-Wallis test (when it do not comply with normality) to check the homogeneity of the characteristics of the subjects between the different groups before the intervention.

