- d. For the comparison of means between the results of both groups we will use the t-Student test of related samples and one-way ANOVA (when they are normal) or Mann-Whitney U test or Wilcoxon W test (when they do not meet the normal).
- e. Chi square test or ANCOVA to analyze the influence of the general characteristics of the sample on the effect of the intervention.
- f. For the reliability analysis of the measuring tools, Cronbach's alpha test will be used.
- g. Regression analysis using the multiple linear model to study the relationship between sets of variables.

A significance index of $p < 0.05$ will be established.

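### Neither the 5% level nor the 80% power is tied to a defined effectiveness claim: no primary outcome, primary visit, multiplicity rule or success rule is named

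*Combined protocol and SAP*

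**What the plan says.** The general objective (section 1) is effectiveness "by means of arthroscopy in pain, range of mobility and functionality". The three domains are not ranked.

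Section 5.2 introduces its list with "The dependent variables of the study are the following" and gives six ROM movements, three orthopaedic tests, VAS pain and the modified Harris scale. None is called primary or secondary. On timing, section 7 states: "Data will be recorded at three times: before surgery, after 4 weeks and after 14 weeks of surgery". Neither post-surgery visit is ranked first.

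The sample-size text (SAP, Size Sample and Feasibility) asks for at least 80% power at p<0.05 and relies on a pilot of 10 subjects: "This pilot study will provide us with the estimates of the mean and variance of the response variable". That variable is not identified. The same section adds "The pilot sample will be part of the final sample to be studied", provided that the protocol and variables do not change. The figure of around 30 per group rests on published sample sizes and feasibility.

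Item d of the inferential analysis reads "For the comparison of means between the results of both groups we will use the t-Student test of related samples and one-way ANOVA", with rank tests as the alternative. It names no outcome, visit or number of tests. The section ends with "A significance index of $p < 0.05$ will be established".

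**The concern.** A significance level and a power are properties of a specified test. Here both values are given, but the outcome, visit and contrast they belong to are not. Two consequences follow.

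First, a reader cannot tell which pattern of results would count as effectiveness, so the chance of a false conclusion is undefined. Under several rules that the text allows, it is above the nominal level.

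Second, the sample-size calculation cannot be done, even after the pilot, until someone picks the variable. Because the pilot subjects may be kept, that choice could be made after seeing data that later count in the main comparison.

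**Working it through.** **The plan's own figure.** Around 30 per group cannot be reproduced, because no outcome, target difference or SD is given. It can be inverted. With 30 per group, two-sided 0.05 and 80% power, the detectable difference is (1.960 + 0.842) × √(2/30) = 0.72 SD, or 0.74 SD with the t distribution. The plan does not say which outcome this would apply to.

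**Count of comparisons.** Assume one between-group test per outcome per post-surgery visit. VAS + Harris + 6 ROM = 8 outcomes, and 8 × 2 visits = 16. If Harris is not taken at 4 weeks, the count is 15. The three orthopaedic tests are left out because item d compares means.

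**False positives favouring the intervention.** Assumptions: two-sided 0.05 tests, so 2.5% in the favourable direction for each, and no true difference.
- Independent tests: 1 − 0.975^k.
- Common correlation ρ: 1 − ∫ φ(x) Φ((1.96 − √ρ·x)/√(1 − ρ))^k dx, integrated numerically.

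The documents give no correlations, so ρ = 0, 0.5 and 0.7 are assumed.

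| Rule (not stated in the plan) | k | ρ = 0 | ρ = 0.5 | ρ = 0.7 |
|---|---|---|---|---|
| Separate claim, pain or function, 14 weeks | 1 | 2.5% | 2.5% | 2.5% |
| Separate claim, pain or function, either visit | 2 | 5% | 4.5% | 4% |
| Separate claim, any of six ROM, 14 weeks | 6 | 14% | 10% | 8% |
| Any of the eight 14-week results | 8 | 18% | 13% | 10% |
| Any result over both visits | 15–16 | 32–33% | 18–19% | 13% |

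For example, 1 − 0.975^6 = 0.141, 1 − 0.975^8 = 0.183 and 1 − 0.975^16 = 0.333. The two-visit row applies to function only if Harris is taken at 4 weeks.

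**All three domains required.** This rule controls the error if each domain has a single 5% test, needs all its measures to be significant, or is itself adjusted (Holm within ROM, or one prespecified ROM summary). Suppose instead that any one of six ROM measures suffices at one visit:
- With no true difference anywhere and independence, 0.025 × 0.025 × 0.141 = 0.00009. At ρ = 0.5 and 0.7 the values are 0.4% and 0.8%. All are below 1%.
- If pain and function truly differ and are almost surely detected, while ROM does not differ, the rule reduces to any-of-six ROM. The false claim then approaches 14%, 10% and 8%.

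**Why the secondary tests need a gate.** A primary at 0.05 plus an ungated Holm family of seven gives 1 − 0.95 × (1 − 0.05/7)^7 ≈ 0.10 for any false claim under independence, in either direction. Testing the seven only after a significant primary holds it at 0.05.

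**The case against.** The strongest reply is that the objective reads naturally as three domain-specific conclusions, each reported separately. On that reading, pain and function at 14 weeks each have one test and no inflation, and even with both visits each stays at 4–5%. This stands. It confines the inflation at a single visit to ROM, where nothing says how many of six movements must improve.

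A reader might go further and infer that the trial carries a false-positive rate of about one in three. The documents do not support that. The 32–33% needs a rule that any one result over both visits suffices, and independence between measurements repeated on the same patients. The plan states no such rule, and the correlated figures are more plausible than the independent ones. Nor do the documents say that the outcome will be chosen from pilot results. They only fail to prevent it.

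It can also be said that 14 weeks is implicitly the main visit, since the programme lasts 14 weeks and individual participation ends then (section 8, G). That makes the missing visit a smaller gap than the missing outcome, but ending is not designation. Likewise, section 2 names the Harris scale only as the instrument for function, beside pain and ROM.

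Finally, the count depends on convention. Including the orthopaedic tests would raise it to 21 or 22.

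**Conclusion.** The gap is real. The supplied text names no primary outcome, primary visit, multiplicity rule or success rule, and the variable used for sizing is unidentified. The 5% level and the 80% power therefore attach to no defined claim.

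How much error this adds cannot be read from the plan. Under the rules considered, the chance of a false favourable claim runs from below 1% (all domains required, no true difference anywhere), through 2.5% (a single pain or function test) and 8–14% (any-of-six ROM), to 13–19% with correlated tests if any result at either visit counts. These figures rest on the assumed decision rules, correlations and one test per outcome per visit.

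The trial can run, but this should be settled before pilot outcomes are examined.

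**What to change.** Before any pilot outcome is examined:

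1. Name one primary outcome at 14 weeks. The choice is the sponsor's; modified Harris or VAS are examples. Base the sample size on it.
2. Compare the groups on it by ANCOVA adjusted for its baseline value, at two-sided 0.05, in place of the item d list. A related-samples t-test addresses change within subjects, not the difference between two groups, and the baseline values are already collected.
3. Test the other seven 14-week pain, function and ROM outcomes with Holm only if the primary is significant, or report them as supportive without a confirmatory claim.
4. Report the 4-week results and the orthopaedic tests as exploratory.

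The cost is edits to section 5.2, the sample-size text and item d, with no new data. Some secondary results with p<0.05 could no longer be claimed, and none if the primary fails. At about 30 per group, an unadjusted t-test detects 0.74 SD on the primary with 80% power. A secondary outcome at the first Holm step (0.05/7) needs 0.94 SD for 80% power on its own test. After the gate, if the primary also has 80% power, the chance of claiming that outcome is 0.8 × 0.8 = 64% when independent, 69% at correlation 0.5 and 71% at 0.7. With an assumed baseline correlation of 0.3 to 0.7, ANCOVA lowers the detectable primary difference to 0.70–0.53 SD.

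Separately, the timing of the Harris scale must be reconciled. Section 5.2 says "The patient will be evaluated with this scale prior to the surgical intervention and 14 weeks after the surgery", whereas section 8, item F repeats the pre-surgery evaluation at 4 weeks, and the text after item G relies on a 4-week Harris comparison.
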